12.3 Grading and Attribution of Adverse Events

Information in this section complies with *ICH Guideline E-6: Guidelines for Good Clinical Practice*; and applies the standards:

- *Guidance for Industry: Toxicity Grading Scale for Healthy Adult and Adolescent Volunteers Enrolled in Preventive Vaccine Clinical Trials (published September 2007)* for allergic local reactions to study procedures.
- The definition of anaphylaxis is described in Table 12.3.1.1b (Clinical Criteria for Diagnosing Anaphylaxis)²⁹
- World Allergy Organization (WAO) Subcutaneous Immunotherapy Systemic Reaction Grading System.⁹ National Cancer Institute (NCI) *Common Terminology Criteria for Adverse Events Version 4.03* (published June 14, 2010) for all other reactions. (This document is referred to herein as the “NCI-CTCAE manual.”)

12.3.1 Grading Criteria

12.3.1.1 Adverse Events Related to Nasal Allergen Challenge, Skin Testing and Immunotherapy

Adverse events related to nasal allergen challenge, skin testing, and immunotherapy not associated with systemic signs or symptoms will be graded according to Table 12.3.1.1a below. All AEs should be recorded on the eCRF.

Table 12.3.1.1a Grading of Local Reactions to Study Procedures

Grade	1	2	3	4
Nasal allergen challenge	Requiring antihistamines, decongestants or nasal steroids as rescue medication	Requiring oral steroids as rescue medication	Requiring a visit to a health care provider for treatment.	Life-threatening and/or requiring hospitalization (e.g. upper airway obstruction)
Skin testing	Meets the minimum criteria listed in section 12.2.1, but requiring no medication other than topical corticosteroids or antihistamines.	Interfering with usual daily activities or sleep and requiring oral steroids.	Requiring a visit to a health care provider for treatment	Not applicable
Immunotherapy	Requires a change in IT dosing, but requiring no medication other than topical corticosteroids or antihistamines.	Interfering with usual daily activities or sleep and requiring oral steroids.	Requiring a visit to a health care provider for treatment	Not applicable

Criteria from Sampson, et al.²⁹ (Table 12.3.1.1b), will be used to determine whether systemic allergic reactions constitute anaphylaxis. To be considered anaphylaxis, the event must involve at least two organ systems (e.g. not be simply a skin reaction).

Table 12.3.1.1b Clinical Criteria for Diagnosing Anaphylaxis

Anaphylaxis is highly likely when any one of the following 3 criteria are fulfilled:


1) Acute onset of an illness (minutes to several hours) with involvement of the skin, mucosal tissue, or both (e.g., generalized hives, pruritus or flushing, swollen lips-tongue-uvula) AND AT LEAST ONE OF THE FOLLOWING:
 
 a) Respiratory compromise (e.g., dyspnea, wheeze-bronchospasm, stridor, reduced PEF, hypoxemia) b) Reduced BP or associated symptoms of end-organ dysfunction (e.g., hypotonia [collapse], syncope, incontinence) 
2) Two or more of the following that occur rapidly after exposure to a likely allergen for that patient (minutes to several hours):
 
 a) Involvement of the skin-mucosal tissue (e.g., generalized hives, itch-flush, swollen lips-tongue-uvula) b) Respiratory compromise (e.g., dyspnea, wheeze-bronchospasm, stridor, reduced PEF, hypoxemia) c) Reduced BP or associated symptoms (e.g., hypotonia [collapse], syncope, incontinence) d) Persistent gastrointestinal symptoms (e.g., crampy abdominal pain, vomiting) 
3) Reduced BP after exposure to known allergen for that patient (minutes or several hours):
 
 a) Infants and children: low systolic BP (age specific) or greater than 30% decrease in systolic BP* b) Adults: systolic BP of less than 90 mm Hg or greater than 30% decrease from that person’s baseline

PEF, Peak expiratory flow; BP, blood pressure. *Low systolic blood pressure for children is defined as less than 70 mm Hg from 1 month to 1 year, less than (70 mm Hg + [2 x age]) from 1 to 10 years, and less than 90 mm Hg from 11 to 17 years.

All anaphylaxis events, regardless of severity grade, and other systemic reactions will be recorded as Adverse Events and will be graded according to Table 12.3.1.1c World Allergy Organization Subcutaneous Immunotherapy Systemic Reaction Grading System.⁹

Table 12.3.1.1c World Allergy Organization Subcutaneous Immunotherapy Systemic Reaction Grading System

World Allergy Organization Subcutaneous Immunotherapy Systemic Reaction Grading System (see text)				
Grade 1	Grade 2	Grade 3	Grade 4	Grade 5

Symptom(s)/ sign(s) of one organ system present
 
Cutaneous
 
Generalized pruritus, urticaria, flushing or sensation of heat or warmth¹
 
or
 
Angioedema (not laryngeal, tongue or uvular)
 
or
 
Upper respiratory
 
Rhinitis (e.g., sneezing, rhinorrhea, nasal pruritus and/or nasal congestion)
 
or
 
Throat-clearing (itchy throat)
 
or
 
Cough perceived to come from the upper airway, not the lung, larynx, or trachea
 
or
 
Conjunctival
 
Conjunctival erythema, pruritus or tearing
 
or
 
Other
 
Nausea, metallic taste, or headache
	
Symptom(s)/ sign(s) of more than one organ system present
 
or
 
Lower respiratory
 
Asthma: cough, wheezing, shortness of breath (e.g., less than 40% PEF or FEV1 drop, responding to an inhaled bronchodilator)
 
or
 
Gastrointestinal
 
Abdominal cramps, vomiting, or diarrhea
 
or
 
Other
 
Uterine cramps
	
Lower respiratory
 
Asthma (e.g., 40% PEF or FEV1 drop, NOT responding to an inhaled bronchodilator)
 
or
 
Upper respiratory
 
Laryngeal, uvula or tongue edema with or without stridor
	
Lower or Upper respiratory
 
Respiratory failure with or without loss of consciousness
 
or
 
Cardiovascular
 
Hypotension with or without loss of consciousness
	
Death

Patients may also have a feeling of impending doom, especially in grades 2, 3, or 4.
 
Note: children with anaphylaxis seldom convey a sense of impending doom and their behavior changes may be a sign of anaphylaxis, e.g., becoming very quiet or irritable and cranky.
				

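### A systemic nasal-challenge reaction that leads to hospitalization can miss the automatic study halt that a local reaction with the same outcome triggers

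*Protocol*

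**What the plan says.** Rule 3 appears in Protocol 11.5, in the protocol synopsis and in SAP section 3. All three halt the study after one Grade 4 local reaction (Table 12.3.1.1a) or one Grade 4 systemic reaction (Table 12.3.1.1c) possibly related to the NAC, pending review by the Medical Monitor and the DSMB.

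Protocol 12.3.1.1 decides which table applies:

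- Reactions without systemic features go to the local table: "Adverse events related to nasal allergen challenge, skin testing, and immunotherapy not associated with systemic signs or symptoms will be graded according to Table 12.3.1.1a".
- Anaphylaxis of any severity goes to the WAO table, and so do the rest: "other systemic reactions will be recorded as Adverse Events and will be graded according to Table 12.3.1.1c".

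Grade 4 has a different basis on each table. For the NAC row of the local table it is "Life-threatening and/or requiring hospitalization (e.g. upper airway obstruction". On the WAO table it is "Respiratory failure with or without loss of consciousness", or hypotension. WAO Grade 3 includes "Laryngeal, uvula or tongue edema with or without stridor" and "Asthma (e.g., 40% PEF or FEV1 drop, NOT responding to an inhaled bronchodilator".

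**The concern.** The protocol already treats one NAC reaction requiring hospitalization as enough to halt the study, provided that the reaction is local. Once the reaction is systemic, and so more extensive, that criterion drops out and only specified signs count. All participants have asthma, and Protocol 5.4.4 names provoked asthma symptoms and anaphylaxis as risks of the challenge. The foreseeable serious reactions are thus graded on the table that lacks the hospitalization criterion.

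At stake is whether challenges in other children pause automatically after such an admission, or only if someone decides that they should.

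**Working it through.** No calculation in the plan bears on this. The check follows each type of NAC reaction through the routing sentences, the tables and rule 3.

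| NAC reaction leading to hospitalization | Table | Grade | Rule 3 halt |
|---|---|---|---|
| Upper airway obstruction, no systemic signs | 12.3.1.1a (local) | 4, by the table's own example | Yes |
| Systemic, with respiratory failure or hypotension | 12.3.1.1c (WAO) | 4 | Yes |
| Generalized hives plus laryngeal edema with stridor | 12.3.1.1c (WAO) | 3 | No |
| Generalized hives plus bronchospasm not responding to a bronchodilator | 12.3.1.1c (WAO) | 3 | No |
| More than one organ system, no Grade 3 or 4 sign | 12.3.1.1c (WAO) | 2 | No |

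**Are rows 3 and 4 really systemic?** Yes. Criterion 1 of Table 12.3.1.1b needs skin or mucosal involvement plus one further feature, and one option is "Respiratory compromise (e.g., dyspnea, wheeze-bronchospasm, stridor, reduced PEF, hypoxemia". Hives with stridor or bronchospasm meets it. Section 12.3.1.1 adds: "To be considered anaphylaxis, the event must involve at least two organ systems". Skin and airway make two.

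**Does another route lead to the local table?** Section 12.2.1 refers NAC responses needing medication to Table 12.3.1.1a. The routing sentences in 12.3.1.1 are more specific, and rule 3 itself calls that table's reactions local.

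**Do rules 1 and 2 close the gap?** No. Rule 1 needs a death at least possibly related to the investigational agent. Rule 2 needs two Grade 4 systemic reactions to injections.

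**What else is lost when rule 3 does not fire?** Section 12.8.2.2 makes an ad hoc DSMB review automatic for occurrences listed in 11.5. Otherwise the protocol chair or sponsor must request it.

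**Counts.** Hospitalization is a criterion in 1 of 4 local NAC grades and 0 of 5 WAO grades. Planned exposure is 80 participants × 2 challenges = up to 160 challenges in randomized children, plus screening challenges in children not randomized. This is exposure, not risk. The cockroach-challenge data in children in Protocol 5.4.4 are 25 children with no reportable adverse event linked to study drug. That gives no usable rate for this event.

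**The case against.** The strongest reply is that the tiers look deliberate: WAO Grade 3 leads to action for the participant and WAO Grade 4 to action for the study. Rule 3 is also already stricter than rule 2, since it needs one event and not two. Two scales with different anchors are not a contradiction. That is fair, but it does not explain why the plan's own hospitalization criterion for NAC reactions lapses when the reaction becomes systemic.

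A reader might infer that such an event would escape oversight. The documents do not support that:

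- A serious adverse event must reach the sponsor within 24 hours, regardless of relationship or expectedness (12.5.1), and the Medical Monitor must review it and decide its disposition (12.8.1).
- A child with Grade 3 anaphylaxis at the screening NAC would be barred from randomization. Section 4.3 excludes a history of anaphylaxis of Grade 3 or higher without reassessment, and 8.5 requires all criteria to be reviewed. The other NAC is at the final visit, so no later dosing is at risk for that child.
- The sponsor or protocol chair can request an ad hoc review, which itself brings a temporary halt (12.8.2.2 and 12.8.2.2.1).
- The challenge is suspended if asthma symptoms appear or peak flow falls by more than 20%, and stopped if FEV₁ is below 85% of baseline (8.1.5). That is well before the 40% drop given as an example in WAO Grade 3.

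These points stand and limit the weight. The first has one exception. Under 12.2.4 an asthma hospitalization is a serious adverse event only if judged a suspected adverse reaction. Section 12.2.2 ties that term to the drug or therapy regimen, whereas 12.2.1 lists the NAC among study procedures. The attribution category of possible in 12.3.2 uses the same reasonable-possibility standard, so most NAC-related asthma admissions should still qualify, but the wording leaves room for argument.

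**Conclusion.** The asymmetry holds on the text. A NAC reaction requiring hospitalization halts the study automatically if it is local. It does not if it is systemic without respiratory failure or hypotension. Only the automatic halt and the automatic ad hoc DSMB review are missed.

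A reader might infer that life-threatening systemic reactions escape rule 3 to the same extent. The documents do not support that. Section 12.2.4 reserves life-threatening for immediate risk of death, and most such systemic reactions will show respiratory failure or hypotension and so be WAO Grade 4. That last step is a clinical assumption. The gap is mainly about hospitalization.

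The conclusion also rests on reading the routing sentences in 12.3.1.1 as governing. If staff would instead put some of these reactions on the local table, the need to clarify remains. The event should be rare and no rate is claimed. The weight is minor: a cheap improvement, not a flaw that undermines the trial.

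**What to change.** In rule 3 of Protocol 11.5, in the synopsis and in SAP section 3, add one line: any reaction possibly related to the NAC that is life-threatening or requires inpatient hospitalization, in the 12.2.4 sense, triggers the halt pending Medical Monitor and DSMB review, whichever table grades it. Leave the WAO scale and rule 2 unchanged.

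The paperwork is a short amendment with IRB approval before use (16.2) and no new data. It helps only while challenges remain to be done.

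The operating cost is a possible extra study-wide pause, including after an admission for observation alone. Enrollment and dosing would stop, and resumption needs the sponsor, DSMB and central IRB to agree (11.5). Lapses can force dose modification (8.6.1), and the only reset of the 40-week escalation limit that the protocol provides is for COVID-19 interruptions (Appendix B). The sponsor should weigh this, but it is the price already accepted for a local NAC reaction with the same outcome.

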12.3.1.2 Grading and Attribution of All Other Adverse Events

The study clinician will grade the severity of other adverse events experienced by the study participants according to the criteria set forth in the National Cancer Institute’s Common Terminology Criteria for Adverse Events (CTCAE) Version 4.0. This document (referred to herein as the NCI-CTCAE manual) provides a common language to describe levels of severity, to analyze and interpret data, and to articulate the clinical significance of all adverse events. The NCI-CTCAE has been reviewed by the Principal Investigators and has been deemed appropriate for the participant population to be studied in this protocol.

Adverse events will be graded on a scale from 1 to 5 according to the following standards in the NCI-CTCAE manual:

- Grade 1 = mild adverse event
- Grade 2 = moderate adverse event
- Grade 3 = severe and undesirable adverse event
- Grade 4 = life-threatening or disabling adverse event
- Grade 5 = death

Events Grade 1 or higher will be recorded on the appropriate AE electronic case report form for this study.

During the course of the study, to determine if an abnormal value or a clinical or laboratory evaluation (including, but not limited to, a radiograph, an ultrasound, an electrocardiogram etc.), is an adverse event will rely on clinical judgment of the study clinician.

For additional information and a printable version of the NCI-CTCAE manual, consult the NCI-CTCAE web site: <http://ctep.cancer.gov/reporting/ctc.html>.

12.3.2 Attribution Definitions

The relationship, or attribution, of an adverse event to the study therapy regimen or study procedure(s) will initially be determined by the study clinician and recorded on the appropriate AE/SAE eCRF. Final determination of attribution for safety reporting will be determined by DAIT NIAID. The relationship of an adverse event to study therapy regimen or procedures will be determined using the descriptors and definitions provided in Table 12.3.2.

For additional information and a printable version of the NCI-CTCAE manual, consult the NCI-CTCAE web site: <http://ctep.cancer.gov/reporting/ctc.html>.

Table 12.3.2 Attribution of Adverse Events

Code	Descriptor	Relationship (to primary investigational product and/or other concurrent mandated study therapy or study procedure)
UNRELATED CATEGORY		
1	Unrelated	The adverse event is clearly not related; there is insufficient evidence to suggest a causal relationship.
RELATED CATEGORIES		
2	Possible	The adverse event has a reasonable possibility to be related; there is evidence to suggest a causal relationship.
3	Definite	The adverse event is clearly related.

12.4 Collection and Recording of Adverse Events

12.4.1 Collection Period

Adverse events (including SAEs) will be collected from the time of consent until 30 days after a participant completes study participation or until 30 days after he/she prematurely withdraws (without withdrawing consent) or is withdrawn from the study.

12.4.2 Collecting Adverse Events

Adverse events (including SAEs) may be discovered through any of these methods:

- Observing the participant
- Interviewing the participant
- Receiving an unsolicited complaint from the subject
- In addition, an abnormal value or result from a clinical or laboratory evaluation can also indicate an adverse event, as defined in Section 12.3, Grading and Attribution of Adverse Events

12.4.3 Recording Adverse Events

Throughout the study, the investigator will record adverse events and serious adverse events as described previously (Section 12.2, Definitions) on the appropriate AE/SAE eCRF regardless of the relationship to study therapy regimen or study procedure.

Once recorded, an AE/SAE will be followed until it resolves with or without sequelae, or until 30 days after the end of study participation, or until 30 days after the subject prematurely withdraws (without withdrawing consent)/or is withdrawn from the study, whichever occurs first. The DAIT NIAID Medical Officer may request continued follow-up of an adverse event beyond the stated timeframe if deemed clinically important.

12.5 Reporting of Serious Adverse Events and Adverse Events

12.5.1 Reporting of Serious Adverse Events to the IND Sponsor (DAIT/NIAID)

This section describes the responsibilities of the Principal Investigator to report serious adverse events to the IND sponsor via SAE eCRF. Timely reporting of adverse events is required by 21 CFR and ICH E6 guidelines.

Principal Investigators must report all serious adverse events (see Section 04, Serious Adverse Event), regardless of relationship or expectedness within 24 hours of becoming aware of the event.

For serious adverse events, all requested information on the AE/SAE eCRF will be provided. The following minimal criteria must be included in the initial SAE eCRF:

- AE Term
- Study Drug Treatment
- Relationship to study drug
- Reason why the event is serious

However, unavailable details of the event will not delay submission of the known information. As additional details become available, the AE/SAE eCRF will be updated and submitted. Every time the SAE eCRF is submitted, it should be electronically signed by the investigator or sub-investigator.

12.5.2 Reporting to FDA

After an adverse event requiring 24 hour reporting (per Section 12.5.1, Reporting of Serious Adverse Events to Sponsor) is submitted by the Principal Investigator and assessed by the IND sponsor (DAIT NIAID), the IND Sponsor (DAIT NIAID) must report the adverse event to the FDA using one of these two options: standard reporting (report in the IND annual report) and expedited safety reporting.

12.5.2.1 Standard Reporting (Report in the IND Annual Report)

This option applies if the AE is classified as one of the following:

- Serious, expected, suspected adverse reactions (see Section 12.2.2, Suspected Adverse Reaction, and Section 12.2.3, Unexpected Adverse Event).
- Serious and not a suspected adverse reaction (see Section 12.2.2, Suspected Adverse Reaction).
- Pregnancies.

Note that all adverse events (not just those requiring 24-hour reporting) will be reported in the IND Annual Report.

12.5.2.2 Expedited Safety Reporting

This option, with 2 possible categories, applies if the adverse event is classified as one of the following:

Category 1: Serious and unexpected suspected adverse reaction [SUSAR] (see Section 12.2.2, Suspected Adverse Reaction (SAR), and Section 12.2.3, Unexpected Adverse Event and 21 CFR 312.32(c)(1)i).

The sponsor must report any suspected adverse reaction that is both serious and unexpected. The sponsor shall report an adverse event as a suspected adverse reaction only if there is evidence to suggest a causal relationship between the study drug and the adverse event, such as:

1. One or more occurrences of an event that is not commonly associated with drug exposure, but is otherwise uncommon in the population exposed to the drug (e.g., tendon rupture);
2. An aggregate analysis of specific events observed in a clinical trial (such as known consequences of the underlying disease or condition under investigation or other events that commonly occur in the study population independent of drug therapy) that indicates those events occur more frequently in the drug treatment group than in a concurrent or historical control group.

Category 2: Any findings from studies that suggests a significant human risk

The sponsor shall report any findings from other epidemiological studies, analyses of adverse events within the current study or pooled analysis across clinical studies or animal or *in vitro* testing (e.g. mutagenicity, teratogenicity, carcinogenicity) that suggest a significant risk in humans exposed to the drug that would result in a safety-related change in the protocol, informed consent, Investigator Brochure or Package Insert or other aspects of the overall conduct of the study.

DAIT NIAID must report to the FDA and notify all participating investigators of expedited Safety Reports within 15 calendar days; unexpected fatal or immediately life-threatening suspected adverse reaction(s) must be reported as soon as possible or within 7 calendar days.

12.5.3 Reporting of Adverse Events to IRBs

All Principal Investigators must report adverse events, including expedited reports, in a timely fashion to the central IRB of record in accordance with applicable regulations and guidelines. All IND Safety Reports to the FDA shall be distributed by the IND sponsor (DAIT NIAID) or designee to all participating institutions for central IRB submission.

12.6 Pregnancy Reporting

The Principal Investigator shall be informed immediately of any pregnancy in a study participant occurring from time of consent through 30 days after the participant completes study participation. A pregnant participant shall be instructed to stop taking study medication. The investigator shall counsel the participant and discuss the risks of continuing with the pregnancy and the possible effects on the fetus. Monitoring of the pregnant participant shall continue until the conclusion of the pregnancy.

The investigator shall report to the DAIT SACCC and the IND sponsor (DAIT NIAID) all pregnancies within 1 business day of becoming aware of the event using the Pregnancy eCRF. All pregnancies identified during the study shall be followed to conclusion and the outcome of each must be reported. The

Pregnancy eCRF shall be updated and submitted to the DAIT SACCC when details about the outcome are available.

Information requested about the delivery shall include:

- Gestational age at delivery
- Birth weight, length, and head circumference
- Gender
- Appearance, pulse, grimace, activity, and respiration (APGAR) score at 1 minute, 5 minutes, and 24 hours after birth, if available
- Any abnormalities

For all pregnancy complications that result in a congenital abnormality, birth defect, miscarriage, and medically indicated abortion, an SAE shall be submitted to the DAIT SACCC and the IND sponsor (DAIT NIAID) using the SAE reporting procedures described above.

